#### 9.6.2 Laboratory Data

Hematology laboratory parameters include white blood cell count, red blood cell count, hemoglobin, hematocrit and platelets, and the differential includes: neutrophils, lymphocytes, monocytes, eosinophils, and basophils.

The chemistry tests includes: Albumin, alkaline phosphatase (ALP), alanine aminotransferase (ALT), aspartate aminotransferase (AST), blood urea nitrogen (BUN), calcium, creatinine, chloride, ferritin, lactate dehydrogenase (LDH), phosphorus, potassium, sodium, total bilirubin, uric acid and lipase, amylase, and hemoglobin A1c (at screening only) and Creatinine Clearance as estimated by the central lab as ~~Glomerular Filtration Rate~~.

Inflammatory serologies include: C-reactive protein (CRP), C3, and C4.

Specialty autoimmune serologies include: Anti-neutrophil cytoplasmic antibodies (ANCA), anti-double-stranded DNA (anti-dsDNA), quantitative immunoglobulins (IgM, IgG, IgA), rheumatoid factor (RF), antinuclear antibodies (ANA), and Direct Coomb's.

Laboratory data values will be converted to standard units by conversion programming. A list of Standard units used to present laboratory data is provided in [Appendix 2](#).

Where laboratory values are categorized into NCI CTCAE version 4.03 grades, the categories are defined according to the criteria available on the following website:

<http://evs.nci.nih.gov/ftp1/CTCAE/About.html>

NCI CTCAE grades will be applied for the following lab parameters (given in [Appendix 3](#)). Laboratory measurements that are within their institutional limits of normal and are not graded as 1-4, per the CTCAE, will be summarized as "Grade 0," which is defined as normal.

Hematology: White blood cell (WBC) count with 5-part differential (neutrophils, lymphocytes, monocytes, eosinophils, and basophils), red blood cell count, platelet count, hemoglobin, and hematocrit.

Chemistry: Albumin, alkaline phosphatase (ALP), alanine aminotransferase (ALT), aspartate aminotransferase (AST), blood urea nitrogen (BUN), calcium, creatinine, chloride, ferritin, lactate dehydrogenase (LDH), phosphorus, potassium, sodium, total bilirubin, uric acid, lipase, and amylase).

Clinical laboratory data (hematology, complete blood count [CBC] with differential, serum chemistry, inflammatory serologies, and specialty autoimmune serologies) will be presented graphically (mean and standard deviation) for selected laboratory tests, by treatment or dose level and scheduled visit. Summary statistics may be tabulated where appropriate. The worst post-baseline NCI CTCAE v4.03 will be presented by treatment or dose level and total for each laboratory test. Subjects with at least one on-study measurement for each laboratory parameter will be included, regardless of whether or not a baseline assessment is present.

Laboratory results and NCI CTCAE grades for hematology, and serum chemistry will be presented in data listings. Normal ranges will be documented and out-of-range values will be flagged by subject listings of grade 3 or higher abnormal lab results. Continuous summaries will be presented by clinical laboratory results, clinical visit, treatment group or dose level and study portion for actual results and changes from baseline. A shift table from baseline to worst observed post-baseline measure will also be presented.

### **9.6.3 ECOG Performance Status**

Shifts from baseline to the best and worst post-baseline score will be tabulated by treatment or dose level.

A by-subject listing of ECOG performance status will be generated.

### **9.6.4 Physical Examinations, Electrocardiogram, and Other Observations Related to Safety**

Clinically significant findings observed during physical examinations will be recorded on the AE and pre-existing condition CRFs. No analyses for physical examinations will be performed.

By-subject listings of weight, height , electrocardiogram (ECG) results, and subsequent cancer-related therapies will be generated.

## **10.0 Validation**

PRA seeks to ensure the quality of the results provided for the study in the form of TFLs, and the derived datasets used in their creation, through the following processes:

The entire set of TFLs will be checked for completeness and consistency prior to its delivery to the client by the lead analysis programmer, the lead statistician, and a senior level statistician, or above, who is not a member of the project team.

The PRA validation process will be repeated any time TFLs are redelivered using different data. Execution of this validation process will be documented through the study Table of Programs that will be provided to Seattle Genetics at study conclusion.

## Appendix 1 Glossary of Abbreviations

### Glossary of Abbreviations:

ADC	Antibody-drug Conjugate
ADI	Absolute Dose Intensity
AE	Adverse event
ALP	Alkaline Phosphatase
ALT	Aminotransferase
AML	Acute Myeloid Leukemia
ANA	Antinuclear Antibodies
ANCA	Anti-neutrophil Cytoplasmic Antibodies
AST	Aspartate Aminotransferase
ATA	Antitherapeutic Antibodies
ATC	Anatomical-Therapeutic Chemical
BSA	Body Surface Area
BUN	Blood Urea Nitrogen
CBC	Complete Blood Count
CMH	Cochran-Mantel-Haenszel
CR	Complete Response
CRF	Case Report Form
CRP	C-reactive Protein
CSR	Clinical Study Report
CTCAE	Common Terminology Criteria for Adverse Events
DLT	Dose-limiting Toxicity
DNA	Deoxyribonucleic Acid
DOR	Duration of Response
ECG	Electrocardiogram
ECOG	Eastern Cooperative Oncology Group
ELISA	Enzyme-linked Immunosorbent Assays
EOT	End of Treatment
HI	Hematologic Improvement
IDMC	Independent Data Monitoring Committee

IPSS	International Prognostic Scoring System
ITT	Intent to Treat
IWG	International Working Group
LDH	Lactate Dehydrogenase
MDS	Myelodysplastic Syndrome
MDSC	Myeloid-Derived Suppressor Cells
MedDRA	Medical Dictionary for Regulatory Activities
MTD	Maximum Tolerated Dose
NCI	National Cancer Institute
ORR	Overall Response Rate
OS	Overall Survival
PBMC	Peripheral Blood Mononuclear Cells
PD	Progressive Disease
PFS	Progression Free Survival
PK	Pharmacokinetic
PNH	Paroxysmal Nocturnal Hemoglobinuria
PR	Partial Response
PRO	Patient Reported Outcome
PT	Preferred Term
QoL	Quality of Life
QLQ	Quality of Life Questionnaire
RDI	Relative Dose Intensity
RF	Rheumatoid Factor
RNA	Ribonucleic Acid
SAP	Statistical Analysis Plan
SAE	Serious Adverse Event
SD	Standard Deviation
SE	Standard Error
SMC	Safety Monitoring Committee
SOC	System Organ Class
TEAE	Treatment-emergent Adverse Event

---

TFL	Tables, Listings, and Figures
WBC	White Blood Cell

## Appendix 2 Laboratory Standard Units

Laboratory Test	Conventional Units
Alanine Transaminase	U/L
Albumin	g/L
Alkaline Phosphatase	U/L
Amylase	U/L
Aspartate Transaminase	U/L
Basophils	$10^9/L$
Bilirubin (Total)	umol/L
Blood Urea Nitrogen	mmol/L
Calcium	mg/dL
Chloride	mmol/L
Creatinine	umol/L
Eosinophils	$10^9/L$
Ferritin	pmol/L
Gamma-glutamyltransferase	U/L
GFR	ml/min
Glucose	mg/dL
Hematocrit	Ratio
Hemoglobin	g/dL
Hemoglobin A1C	%
International normalized ratio	%
Lactate Dehydrogenase	U/L
Lipase	U/L
Lymphocytes	$10^9/L$
Magnesium	mg/dL
Monocytes	$10^9/L$
Total Neutrophils	$10^9/L$
Partial Thromboplastin Time	seconds
Phosphorous	mmol/L
Platelets	$10^9/L$
Potassium	mmol/L
Prothrombin Time	seconds
Sodium	mmol/L
Uric Acid	mmol/L
White Blood Cells	$10^9/L$
Red Blood Cells	$10^{12}/L$

### Appendix 3 CTCAE v4.03 Grading for Laboratory Values and QTc

CTCAE v4.03 SOC	CTCAE v4.03 Term	Grade 1	Grade 2	Grade 3	Grade 4
Investigations	White blood cell decreased	<LLN - 3000/mm  ; <LLN - 3.0 × 10  /L	<3000 - 2000/mm  ; <3.0 - 2.0 × 10  /L	<2000 - 1000/mm  ; <2.0 - 1.0 × 10  /L	<1000/mm  ; <1.0 × 10  /L
Investigations	White blood cell increased (leukocytosis)	-	-	>100,000 mm 	Clinical manifestations of leucostasis; urgent intervention indicated
Blood and lymphatic system disorders	Anemia	Hemoglobin (Hgb) <LLN - 10.0 g/dL; <LLN - 6.2 mmol/L; <LLN - 100 g/L	Hgb <10.0 - 8.0 g/dL; <6.2 - 4.9 mmol/L; <100 - 80g/L	Hgb <8.0 g/dL; <4.9 mmol/L; <80 g/L; transfusion indicated	Life-threatening consequences; urgent intervention indicated
Investigations	Lymphocyte count decreased	<LLN - 800/mm  ; <LLN - 0.8 × 10  /L	<800 - 500/mm  ; <0.8 - 0.5 × 10  /L	<500 - 200/mm  ; <0.5 - 0.2 × 10  /L	<200/mm  ; <0.2 × 10  /L
Investigations	Lymphocyte count increased	-	>4000 - 20,000 mm 	>20,000 mm 	-
Investigations	Neutrophil count decreased	<LLN - 1500/mm  ; <LLN - 1.5 × 10  /L	<1500 - 1000/mm  ; <1.5 - 1.0 × 10  /L	<1000 - 500/mm  ; <1.0 - 0.5 × 10  /L	<500/mm  ; <0.5 × 10  /L
Investigations	Platelet count decreased	<LLN - 75,000/mm  ; <LLN - 75.0 × 10  /L	<75,000 - 50,000/mm  ; <75.0 - 50.0 × 10  /L	<50,000 - 25,000/mm  ; <50.0 - 25.0 × 10  /L	<25,000/mm  ; <25.0 × 10  /L
Metabolism and nutrition disorders	Hypoalbuminemia	<LLN - 3 g/dL; <LLN - 30 g/L	<3 - 2 g/dL; <30 - 20 g/L	<2 g/dL; <20 g/L	Life-threatening consequences; urgent intervention indicated
Investigations	Alkaline phosphatase increased	>ULN - 2.5 × ULN	>2.5 - 5.0 × ULN	>5.0 - 20.0 × ULN	>20.0 × ULN
Investigations	Alanine aminotransferase	>ULN - 3.0 × ULN	>3.0 - 5.0 × ULN	>5.0 - 20.0 × ULN	>20.0 × ULN

CTCAE v4.03 SOC	CTCAE v4.03 Term	Grade 1	Grade 2	Grade 3	Grade 4
	se increased				
Investigations	Aspartate aminotransferase increased	>ULN - 3.0 x ULN	>3.0 - 5.0 x ULN	>5.0 - 20.0 x ULN	>20.0 x ULN
Investigations	Blood bilirubin increased	>ULN - 1.5 x ULN	>1.5 - 3.0 x ULN	>3.0 - 10.0 x ULN	>10.0 x ULN
Investigations	GGT increased	>ULN - 2.5 x ULN	>2.5 - 5.0 x ULN	>5.0 - 20.0 x ULN	>20.0 x ULN
Investigations	Hemoglobin increased	Increase in >0-2 gm/dl above ULN or above baseline if baseline is above ULN	Increase in >2-4 gm/dl above ULN or above baseline if baseline is above ULN	Increase in >4 gm/dl above ULN or above baseline if baseline is above ULN	-
Investigations	INR increased	>1-1.5 x ULN; >1-1.5 times above baseline if on anticoagulation	>1.5-2.5 x ULN; >1.5-2.5 times above baseline if on anticoagulation	>2.5 x ULN; >2.5 times above baseline if on anticoagulation	-
Investigations	Prolonged PTT	>ULN - 1.5 x ULN	>1.5 - 2.5 x ULN	>2.5 x ULN; hemorrhage	-
Metabolism and nutrition disorders	Hypercalcemia	Corrected serum calcium of >ULN - 11.5 mg/dL; >ULN - 2.9 mmol/L; Ionized calcium >ULN - 1.5 mmol/L	Corrected serum calcium of >11.5 - 12.5 mg/dL; >2.9 - 3.1 mmol/L; Ionized calcium >1.5 - 1.6 mmol/L; symptomatic	Corrected serum calcium of >12.5 - 13.5 mg/dL; >3.1 - 3.4 mmol/L; Ionized calcium >1.6 - 1.8 mmol/L; hospitalization indicated	Corrected serum calcium of >13.5 mg/dL; >3.4 mmol/L; Ionized calcium >1.8 mmol/L; life-threatening consequences
Metabolism and nutrition disorders	Hypocalcemia	Corrected serum calcium of <LLN - 8.0 mg/dL; <LLN - 2.0 mmol/L; Ionized calcium <LLN - 1.0 mmol/L	Corrected serum calcium of <8.0 - 7.0 mg/dL; <2.0 - 1.75 mmol/L; Ionized calcium <1.0 - 0.9 mmol/L; symptomatic	Corrected serum calcium of <7.0 - 6.0 mg/dL; <1.75 - 1.5 mmol/L; Ionized calcium <0.9 - 0.8 mmol/L; hospitalization indicated	Corrected serum calcium of <6.0 mg/dL; <1.5 mmol/L; Ionized calcium <0.8 mmol/L; life-threatening consequences

CTCAE v4.03 SOC	CTCAE v4.03 Term	Grade 1	Grade 2	Grade 3	Grade 4
Investigations	Creatinine increased	>1 - 1.5 × baseline; >ULN - 1.5 × ULN	>1.5 - 3.0 × baseline; >1.5 - 3.0 × ULN	>3.0 baseline; >3.0 - 6.0 × ULN	>6.0 × ULN
Metabolism and nutrition disorders	Hyperglycemia	Fasting glucose value >ULN - 160 mg/dL; Fasting glucose value >ULN - 8.9 mmol/L	Fasting glucose value >160 - 250 mg/dL; Fasting glucose value >8.9 - 13.9 mmol/L	>250 - 500 mg/dL; >13.9 - 27.8 mmol/L; hospitalization indicated	>500 mg/dL; >27.8 mmol/L; life-threatening consequences
Metabolism and nutrition disorders	Hypoglycemia	<LLN - 55 mg/dL; <LLN - 3.0 mmol/L	<55 - 40 mg/dL; <3.0 - 2.2 mmol/L	<40 - 30 mg/dL; <2.2 - 1.7 mmol/L	<30 mg/dL; <1.7 mmol/L; life-threatening consequences; seizures
Metabolism and nutrition disorders	Hypermagnesemia	>ULN - 3.0 mg/dL; >ULN - 1.23 mmol/L	-	>3.0 - 8.0 mg/dL; >1.23 - 3.30 mmol/L	>8.0 mg/dL; >3.30 mmol/L; life-threatening consequences
Metabolism and nutrition disorders	Hypomagnesemia	<LLN - 1.2 mg/dL; <LLN - 0.5 mmol/L	<1.2 - 0.9 mg/dL; <0.5 - 0.4 mmol/L	<0.9 - 0.7 mg/dL; <0.4 - 0.3 mmol/L	<0.7 mg/dL; <0.3 mmol/L; life-threatening consequences
Metabolism and nutrition disorders	Hypophosphatemia	<LLN - 2.5 mg/dL; <LLN - 0.8 mmol/L	<2.5 - 2.0 mg/dL; <0.8 - 0.6 mmol/L	<2.0 - 1.0 mg/dL; <0.6 - 0.3 mmol/L	<1.0 mg/dL; <0.3 mmol/L; life-threatening consequences
Metabolism and nutrition disorders	Hyperkalemia	>ULN - 5.5 mmol/L	>5.5 - 6.0 mmol/L	>6.0 - 7.0 mmol/L; hospitalization indicated	>7.0 mmol/L; life-threatening consequences
Metabolism and nutrition disorders	Hypokalemia	<LLN - 3.0 mmol/L	<LLN - 3.0 mmol/L; symptomatic; intervention indicated	<3.0 - 2.5 mmol/L; hospitalization indicated	<2.5 mmol/L; life-threatening consequences
Metabolism and nutrition disorders	Hyponatremia	<LLN - 130 mmol/L	-	<130 - 120 mmol/L	<120 mmol/L; life-threatening consequences
Metabolism and nutrition disorders	Hypernatremia	>ULN - 150 mmol/L	>150 - 155 mmol/L	>155 - 160 mmol/L; hospitalization indicated	>160 mmol/L; life-threatening consequences
Metabolism and nutrition disorders	Hyperuricemia	>ULN - 10 mg/dl (0.59 mmol/L) without physiologic	-	>ULN - 10 mg/dl (0.59 mmol/L) with physiologic consequences	>10 mg/dl ; >0.59 mmol/L; life-threatening consequences

CTCAE v4.03 SOC	CTCAE v4.03 Term	Grade 1	Grade 2	Grade 3	Grade 4
		consequences			
Electrocardiogram QT corrected interval prolonged		QTc 450 - 480 ms	QTc 481 - 500 ms	QTc >= 501 ms	

### Appendix 4 Imputation of Partially Unknown Adverse Event Dates

The algorithm below should be used to impute pre-existing condition and adverse event (AE) start dates for which only partial information is known. For ease of reading, both pre-existing conditions and AEs will be referred to as AE for the remainder of this document. The algorithm should be applied to every AE record on a record by record basis. AE start dates should be imputed before imputation of AE condition end date in all cases. The AE condition end date should only be used in the imputation of the AE start date if it a full known date.

#### AE day and month are missing

If the year is the same as the year of first dose of investigational agent and the onset period and/or onset time indicate that the start of the AE was pre-dose:

AE start date will be imputed as the minimum of (AE condition end date\*, day prior to first dose of investigational agent)

If the year is the same as the year of first dose of investigational agent and the onset period and/or onset time indicate that the start of the AE was post-dose:

AE start date will be imputed as the minimum of (AE condition end date\*, first dose date of investigational agent)

If the year is before the year of first dose of investigational agent:

AE start date will be imputed as the minimum of (AE condition end date\*, December 31st see example 2 below)

If the year is after the year of first dose of investigational agent:

AE start date will be imputed as the minimum of (AE condition end date\*, January 31st see example 2 below)

#### AE month only is missing

Treat day as missing and replace both month and day according to the above procedure

#### AE day only is missing

If the month/year is the same as the month/year of first dose of investigational agent and the onset period and/or onset time indicate that the start of the AE was pre-dose:

AE start date will be imputed as the minimum of (AE condition end date\*, day prior to first dose of investigational agent)

If the month/year is the same as the month/year of first dose of investigational agent and the onset period and/or onset time indicate that the start of the AE was post-dose:

AE start date will be imputed as the minimum of (AE condition end date\*, first dose date of investigational agent)

If the month/year is before the month/year of first dose of investigational agent:

AE start date will be imputed as the minimum of (AE condition end date\*, last day of the month)

If the month/year is after the month/year of first dose of investigational agent:

AE start date will be imputed as the minimum of (AE condition end date\*, last day of the month)

\* only use condition end date if known and full end date is available.

The following algorithm should be used to impute AE condition end dates. The AE records for a condition/event should be sorted by the imputed start dates then record position (order of entry into the eCRF). After sorting, if any condition end date month/year is greater than any subsequent record end date month/year, then change the imputed start day only to end of month. Repeat as necessary.

After sorting the AE records, apply the following rules to partial or missing AE condition end dates:

**For all records excluding the last chronological record for a condition/event**

AE condition end date will be imputed as the start date of the subsequent record

**For the last chronological record for a condition/event**

If outcome is “recovered/resolved”, “recovered/resolved with sequelae”, or “fatal” apply the following:

- If only year is provided for the end date and year is equal to the year of the last dose date:
  - AE condition end date will be imputed as the minimum of (last dose date + 30, death date, data extraction date, December 31st of the end date year)
- If only year is provided for the end date and year is not equal to the year of the last dose date:
  - AE condition end date will be imputed as the minimum of (death date, data extraction date, December 31st of the end date year)
- If month and year are provided for the end date:
  - AE condition end date will be imputed as the minimum of (death date, data extraction date, last day of the end date month/year)

If outcome is “recovering/resolving”, “not recovered/resolved”, “unknown”, or blank: AE condition end date will not be imputed.

**Example 1**

**AESPID 1: Condition/Event HEADACHE**

**First dose date 01JAN2012**

**Prior to imputation**

Start date	Condition end date	Severity	Outcome	Onset
UNUNK2011	15APR2012	1	not recovered/resolved	pre-ICF
15APR2012	UNMAY2012	2	recovering/resolving	post 1st dose
UNMAY2012	UNJUN2012	1	not recovered/resolved	post 1st dose
UNJUN2012	UNJUN2012	3	recovering/resolving	post 1st dose
UNJUN2012	10JUL2012	2	recovering/resolving	post 1st dose
10JUL2012	--	1	not recovered/resolved	post 1st dose

**Post imputation**

Start date	Condition end date	Severity	Outcome
31DEC2011	15APR2012	1	not recovered/resolved
15APR2012	31MAY2012	2	recovering/resolving
31MAY2012	30JUN2012	1	not recovered/resolved
30JUN2012	30JUN2012	3	recovering/resolving
30JUN2012	10JUL2012	2	recovering/resolving
10JUL2012	--	1	not recovered/resolved

**Example 2 (highlights choice of last day of the month as opposed to the 1st or the 15th)**

**AESPID 4: Condition/Event NAUSEA**

**First dose date 01APR2012**

**Prior to imputation**

Start date	Condition end date	Severity	Outcome	Onset
UNUNK2011	25APR2012	1	not recovered/resolved	pre-ICF
25APR2012	UNAPR2012	2	recovering/resolving	post 1st dose
UNAPR2012	04MAY2012	1	recovered/resolved	post 1st dose

**Post imputation**

Start date	Condition end date	Severity	Outcome
31DEC2011	25APR2012	1	not recovered/resolved
25APR2012	31APR2012	2	recovering/resolving
31APR2012	04MAY2012	1	recovered/resolved

### Appendix 5 Treatment Emergent Adverse Event Programming Guide

Term	Standard Definition
Treatment emergent	
Any newly occurring or worsening AE, where newly occurring means an AE that was not present at baseline. Eg, if the patient had a grade 1 headache at baseline that resolved and later had another grade 1 headache, that second headache would NOT be considered a TEAE. See below for more algorithm details.
 
Where:
 
 
1. Get first dose date/time of any study treatment-(the earliest of Azacitidine or vadastuximab talirine/placebo)
 
2. Define baseline AEs as AEs with: 
 
• an onset period of (“started before the signing of informed consent”, or “started after consent but before the first dose of any study treatment”. If the onset period of the AE is missing, then look for AE start date < first dose date (from 1). If AE start date is missing, use AE start date imputation rule.
 
 
<AND>
 
 
• a stop date that is: 
 
➢ <math>\geq</math> first dose date <OR>
 
➢ missing with outcome equal to 
 
▪ recovering/resolving (this outcome may or may not have a date with it), or
 
▪ not recovered/not resolved, or
 
▪ unknown
 
▪ Note: AEs with no outcome and missing stop dates should be queried.
 
 
 
 
 
• Note: If the event ended on Day 1 (the day of first dose) it will be considered a baseline event.
 
 
3. Define post-baseline AEs as AEs with an onset period of (“started after the first dose of any study treatment”. If the onset period of the AE is missing, then look for AE start date <math>\geq</math> first dose date (from 1). If AE start date is missing, use AE start date imputation rule.
 
4. Compare post-baseline AEs to baseline AEs using lower level term (LLT). 
 
• If terms match from baseline to post-baseline: 
 
➢ Compare CTC grades. If post-baseline CTC grade is > baseline CTC grade, then TEAE=YES. If post-baseline CTC grade is <math>\leq</math> Baseline CTC grade, then TEAE=NO.
 
 
 
• If there are no matching terms from baseline to post-baseline, then TEAE=Yes.
 
 
 

	

• If post-baseline AEs are uncoded, then TEAE = Yes.

 
NOTE: if TEAE = 1 or . then include in output, i.e. only exclude TEAE= 0 for “Treatment-emergent” outputs.

--	--

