13.6.7 Safety

Safety data will be summarized for the safety population separately for the Phase 1 and Phase 2 Portions by treatment arm or dose level.

Exposure to treatment will be summarized separately for vadastuximab and azacitidine. Summaries will include the duration of treatment, number of doses received, number of cycles received, number of doses interrupted and the reasons for dose interruption, the number of subjects with dose decreases for toxicity, the cumulative dose, and the relative dose intensity.

All AEs reported after initiation of treatment and pre-existing conditions that worsen after initiation of treatment will be considered treatment-emergent AEs (TEAEs). All AEs will be coded by system organ class, MedDRA preferred term, and severity grade using NCI CTCAE (v 4.03; [Appendix 18.4](#)). All recorded AEs will be included in the data listings.

The number and percent of subjects reporting all TEAEs, treatment-related AEs, SAEs, and deaths; TEAEs according to worst CTCAE grade; and AEs leading to treatment discontinuation will be summarized by preferred term and, where appropriate, system organ class. Deaths, SAEs, and AEs leading to treatment discontinuation will also be listed.

Adverse events that were considered DLTs will be listed and summarized by dose level for the DLT-evaluable population.

Summary statistics for actual values and for change from baseline will be tabulated as appropriate for laboratory results by scheduled visit. Where appropriate, laboratory results will be graded according to CTCAE 4.03, and shift tables from baseline to worst observed posttreatment grade will be presented.

All medications received during the treatment period will be considered as concomitant medications and will be coded by WHO medical dictionary and summarized.

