#### 9.6.1.2 Adverse Events and Serious Adverse Events

AEs will be summarized by descending frequency of MedDRA PT unless otherwise specified. For incidence reporting, if a subject reports more than one AE that was coded to the same SOC or PT, the subject will be counted only once for that specific SOC or PT. See [Section 5](#) for definition of pre-existing AEs, TEAEs, related AEs, SAEs, infusion-related reaction AEs and AEs leading to vadastuximab talirine treatment discontinuation. All the AEs summarized in tables are TEAEs, except related AEs or unless otherwise indicated. All AEs will be coded by SOC, MedDRA PT, and severity grade using NCI CTCAE. All recorded AEs will be included in the data listings.

A summary table of number and percent of the following AE categories will be provided by treatment or dose level and total as follows:

- Pre-existing AEs
- All TEAEs
- TEAEs related to vadastuximab talirine or placebo
- TEAEs related to azacitidine treatment
- TEAEs with outcome of death
- Treatment-emergent SAEs
- Treatment-emergent SAEs related to vadastuximab talirine or placebo
- Treatment-emergent SAEs related to azacitidine treatment

- TEAEs leading to dose delay of vadastuximab talirine or placebo treatment
- TEAEs leading to dose delay of azacitidine treatment
- TEAEs leading to dose interruption (full dose received) of vadastuximab talirine or placebo treatment
- TEAEs leading to dose interruption (full dose received) of azacitidine treatment
- TEAEs leading to dose being stopped early (full dose not received) of vadastuximab talirine or placebo treatment
- TEAEs leading to dose being stopped early (full dose not received) of azacitidine treatment
- TEAEs leading to dose reduction of vadastuximab talirine or placebo treatment
- TEAEs leading to dose reduction of azacitidine treatment
- TEAEs leading to treatment discontinuation
- Treatment-emergent SAEs leading to treatment discontinuation
- Vadastuximab Talirine -related TEAEs leading to treatment discontinuation
- Azacitidine -related TEAEs leading to treatment discontinuation
- Grade 3-5 TEAEs
- Grade 3-5 vadastuximab talirine or placebo treatment-related TEAEs
- Grade 3-5 azacitidine treatment-related TEAEs
- Infusion-related reaction TEAEs

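### SAP Appendix 5 codes a new onset after a resolved baseline event as not treatment-emergent when its grade is no higher, against the TEAE definition in Protocol 13.6.7 and SAP Section 5

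*SAP*

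**What the plan says.** Protocol 13.6.7 sets the definition: "All AEs reported after initiation of treatment and pre-existing conditions that worsen after initiation of treatment will be considered treatment-emergent AEs (TEAEs". SAP Section 5 repeats it and refers to Appendix 5 for the detailed handling of pre-existing events.

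Appendix 5 then narrows it. There, "newly occurring means an AE that was not present at baseline". Its worked example takes a baseline grade 1 headache that went away and a later grade 1 headache, and says "that second headache would NOT be considered a TEAE". The steps behind the example are:

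- Step 2: a baseline AE is one that began before first dose and either stopped on or after the first-dose date or has no stop date and an unresolved or unknown outcome. A note adds: "If the event ended on Day 1 (the day of first dose) it will be considered a baseline event".
- Step 4: "Compare post-baseline AEs to baseline AEs using lower level term (LLT"). If the terms match and the post-baseline grade is at or below the baseline grade, the rule ends "Baseline CTC grade, then TEAE=NO".
- The closing note tells the programmer to "only exclude TEAE= 0 for" treatment-emergent outputs.

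SAP 9.6.1.2 rests the tables on this flag: "All the AEs summarized in tables are TEAEs, except related AEs or unless otherwise indicated". Its categories include treatment-emergent SAEs and grade 3-5 TEAEs. SAP 1.1, which lists changes from the protocol, covers disposition and hematologic improvement and does not mention TEAEs.

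**The concern.** A headache that starts after first dose, once the baseline headache has cleared, is an event reported after treatment began. It is therefore a TEAE under the protocol and SAP Section 5, and not one under Appendix 5. Both rules are in force and the programmer will follow Appendix 5.

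The affected events are relevant to this drug. Protocol 12.1.1 requires all conditions present predose on Day 1 to be recorded, so matching baseline terms will exist. Exclusion criterion 5 admits subjects with controlled or resolving infection, and Protocol 7.1 describes cytopenias as part of the disease. Protocol 7.2 lists febrile neutropenia (70%), anemia (26%) and thrombocytopenia (24%) among the common monotherapy AEs. A recurrence of a condition that had cleared is something a safety table should show. Seriousness plays no part in step 4, so a serious recurrence can also leave the SAE table. Protocol 13.6.7 plans the SAE summary without any treatment-emergent restriction.

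**Working it through.** The plan states no figure for this point, so the check is of the rules themselves.

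**1. Which earlier events can trigger the exclusion (step 2).** Take an event with onset before first dose and first dose on Day 1.

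- Stopped before Day 1: not a baseline AE, so a later recurrence is a TEAE.
- Stopped on Day 1 or later (for example Day 10): a baseline AE, so a later recurrence goes to the grade comparison.

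Only events still present at first dose are involved.

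**2. What the grade comparison removes (step 4).** With a matching lower level term there are 4 baseline grades (1-4) and 5 post-baseline grades (1-5), giving 4 x 5 = 20 pairs. A pair is excluded when the post-baseline grade is no higher than the baseline grade.

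| | Pairs | Excluded | Which (baseline-post) |
|---|---|---|---|
| All | 20 | 1+2+3+4 = 10 | see next two rows |
| Same grade | 4 | 4 | 1-1, 2-2, 3-3, 4-4 |
| Lower post-baseline grade | 6 | 6 | 2-1, 3-1, 3-2, 4-1, 4-2, 4-3 |
| Post-baseline grade 3-5 | 4 x 3 = 12 | 3 | 3-3, 4-3, 4-4 |
| Post-baseline grade 5 | 4 | 0 | none |

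Under the Protocol 13.6.7 wording, a new onset after first dose is a TEAE at any grade, so none of the 20 would be excluded. These are logical cases, not frequencies: 10 of 20 does not mean that half of recurrences are lost.

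**3. Is resolution tested anywhere?** No. Step 4 uses only the term and the grade. The example, in which the first headache has resolved, confirms that this is intended.

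**4. Which outputs change.** Summary tables built on TEAEs lose the record. The listings in SAP 9.6.1.2 and 9.6.1.3 keep it. The worst-grade and shift tables for laboratory values in SAP 9.6.2 do not use the flag. SAP 9.6.1.2 counts a subject once per preferred term, so the subject is missing from a row only if no other TEAE has that term. The effect on related-AE tables is unclear: 9.6.1.2 exempts related AEs from the restriction, yet its own list labels them TEAEs.

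**5. Can a stop date identify resolution?** No. In SAP Appendix 4, Example 2, first dose is 01APR2012. Grade 1 nausea present at baseline has a record ending 25APR2012 with outcome not recovered/resolved. A grade 2 record follows, then a grade 1 record imputed to start at the end of April. This is one continuing condition returning to its baseline grade, although its last record starts after the first record's stop date. A rule based on stop date alone would wrongly call that record a new TEAE.

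**The case against.** The strongest defense is that Appendix 5 is the detailed rule to which Section 5 refers, and that Protocol 13.3 expects the SAP to expand on the protocol. Severity changes are entered as separate records, many dated after first dose. Taken literally, the protocol sentence would turn even an improving baseline condition into a TEAE, so some grade comparison is needed. The rule is also explicit and has a worked example.

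The need for a grade comparison stands, but only for a condition that is still continuing. The cross-reference covers pre-existing events, and a new onset after resolution is not one. The worked example shows that the departure is deliberate, which makes its absence from SAP 1.1 harder to excuse.

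The objection also limits the scope, and this part stands. Much of the information survives elsewhere: listings are complete, deaths are counted separately, laboratory tables cover the count-based cytopenias, and the safety parameters named for the IDMC in Protocol 13.6.10 are not confined to TEAEs. Toxicity that rises above the baseline grade is still counted.

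**Conclusion.** The contradiction is real and undeclared. Relative to the protocol definition, the exclusion of new onsets after resolution can only lower counts in the TEAE summary tables. It reaches treatment-emergent SAEs whose grade is at or below baseline, and grade 3-4 events whose matching baseline grade was at least as high. It does not reach fatal events, events whose earlier episode ended before first dose, the listings or the laboratory shift tables.

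The size cannot be determined, because the documents give neither baseline AE rates nor recurrence rates. If one assumed that 10%-30% of subjects have a given event ongoing at baseline and that 20%-40% of those resolve and recur at the same grade, the product would be 0.10 x 0.20 = 2% to 0.30 x 0.40 = 12%. A reader might take that as the share of subjects missing from a row. The documents support neither input, and once-per-term counting makes the product an upper bound for same-grade recurrences even if both were right.

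A reader might also infer that grade 3-5 events are undercounted across the board, or that the rule hides an excess in the vadastuximab talirine arm. The first fails on the 3 of 12 pairs shown above. The second would require more such recurrences in that arm, which is plausible but not shown. The conclusion rests on the rule texts and on no assumed rate.

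**What to change.** In Appendix 5 step 4, apply the grade comparison only while the baseline condition is unresolved. Judge resolution from the last linked record of that condition, using the condition/event identifier together with an outcome of recovered/resolved or recovered/resolved with sequelae. Do not judge it from a record's stop date alone. Flag a new onset after that resolution as a TEAE at any grade. Delete or reverse the headache example and bring the meaning of newly occurring into line.

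If the sponsor prefers the narrower convention, SAP Section 5 should state it and SAP 1.1 should declare it as a change from Protocol 13.6.7.

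The cost is one revised programming rule, made by SAP amendment before database lock. It uses the outcome and linkage fields already shown in the Appendix 4 examples. TEAE counts will be slightly higher, and programmers should check that sites enter a recurrence after resolution as a new onset.
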